AE/SAE recording	X	X	X	X	X	X	X	X		X		X		X		X		X		X		X		X		X		X	X	X	X	
Urinalysis q	X							X						X						X								X			X	
Serum immunoglobulins (IgG, IgM, IgA)	X							X						X						X								X			X	
Systemic drug concentration (functional dupilumab) r		X	X	X		X		X		X				X						X								X	X	X	X	
Anti-drug antibodies r		X						X						X														X			X	
Biomarker set s		X						X						X						X								X				
Periostin		X		X				X																				X				
Antigen-specific IgE		X						X						X														X				

	S C R a	Randomized Treatment Period																								Post-treatment Period					
		R N D c																							E O T b	E O S					
Week	-4± 1	0	2	4	6	8	10	12	14	16	18	20	22	24	26	28	30	32	34	36	38	40	42	44	46	48	50	52	56	60	64
Visit	1	2	3	4	5	6	7	8	9	10	11	12	13	14	15	16	17	18	19	20	21	22	23	24	25	26	27	28	29	30	
Archival serum f		x						x						x						x								x			
Pharmacogenetics: blood samples for DNA and RNA u		x																													
EQ-5D-5L		x						x						x						x								x		x	
HADS v		x						x						x						x								x		x	
SNOT-22 w		x						x						x						x								x		x	
RQLQ(S) +12 x		x						x						x						x								x		x	
Vaccine IgG	x y				z	z	z	z		z		z		z		z		z		z		z		z		z		z			

- a The Screening Period is 4±1 weeks (21-35 days) in duration to collect baseline data on asthma control and assure eligibility criteria.
- b Patients who permanently discontinue treatment early will continue the remaining visits per protocol schedule with a +/-5 day window until end of study (See section 1.3). At the time of permanent treatment discontinuation the patients will perform early treatment discontinuation (ETD) visit with all the assessments defined for Visit 18 (EOT).
- c Randomization Visit (Visit 2) is defined as Day 1. Visit windows for subsequent visits are +/- 3 days.
- d Three attempts may be made during the Screening Period until the Baseline visit to meet the qualifying criteria for reversibility. During the treatment period, post-bronchodilator FEV1 will be determined at the designated treatment visits. If other attempt for reversibility test was performed at Baseline visit, then the post-bronchodilator FEV1 will come from the result of this reversibility test.

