#### **9.3.4 Vaccine response**

Patients will be encouraged to provide vaccination plans for the following vaccines, tetanus (alone or combined), any injectable influenza, any pneumococcal and any meningococcal, which are in line with the patients age and local medical practice (live attenuated vaccines are excluded) during the study. Subjects planning to receive any of the above listed vaccines during the study may optionally sign a separate informed consent for collection of 2 blood samples for assay of vaccine IgG in serum for each vaccine: the first should be drawn within 6 weeks prior to vaccination and then the second should be drawn 3 to 4 weeks after vaccination (up to 6 weeks afterward allowed). Vaccinations should preferably occur after completion of at least 12 weeks of treatment, while remaining in compliance with the patient’s recommended immunization schedule. Pre-vaccine blood sample collection will not take place until patient is on treatment of IMP for at least 6 weeks. Blood collections should be conducted at regularly scheduled study visits but, if this is not feasible, could also be done at unscheduled visits. The details on the date(s) of vaccination and the specific vaccines that are administered, such as brand and antigenic strains, should be collected (see Appendix L).

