#### **10.1.5 Visit 5 (Week 6)**

- Record all concomitant medication use; inquire about AEs/SAEs and background asthma therapy tolerability
- Measure vital signs (blood pressure, heart rate, respiration rate, body temperature, weight for all patients and height for adolescents only)
- Administer ACQ-7
- Perform spirometry
  - Spirometry will be performed at approximately the same time of last visit after a wash out period of bronchodilators according to their action duration, for example, withholding the last dose of salbutamol/albuterol or levosalbutamol/levalbuterol for at least 6 hours and withholding the last dose of LABA for at least 12 hours (ultra-long acting LABA like vilanterol should be withheld for at least 24 hours) and withholding the last dose of LAMA for at least 24 hours and prior to administration of investigational product. This will be verified before performing the measurements.
- Perform blood sampling for the following test:

- Blood sample for pre-vaccine IgG for patients who have signed a specific informed consent for vaccine assessment and who plan to receive a vaccine in the coming 6 weeks (refer to Section 9.3.4)
- Download electronic diary/PEF meter and remind patient to bring the device to the next visit
- Call IVRS/IWRS to register visit and obtain treatment kit number
- Dispense and administer IMP
  - Patients will be monitored at the study site for a minimum of 30 minutes after the injection.
  - For those patients willing and trained to perform self-injection: The patient (or caregiver) will perform the injection of IMP under the supervision of the Investigator or delegate.
- Remind patients to use salbutamol/albuterol or levosalbutamol/levalbuterol as reliever medication throughout the study. Instruct patient to record usage in the electronic diary.
- Remind patient to continue their stable dose of ICS in combination with one or two other controllers as used during the screening period and instruct patient to record daily usage in the electronic diary.
- Remind patient to withhold bronchodilators according to their action duration, for example, withhold last dose of salbutamol/albuterol or levosalbutamol/levalbuterol for at least 6 hours and withhold last dose of LABA for at least 12 hours (ultra-long acting LABA like vilanterol should be withheld for at least 24 hours) and withhold the last dose of LAMA for at least 24 hours prior to next visit.

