#### **10.1.6 Visit 6 (Week 8)**

- Record all concomitant medication use; inquire about AEs/SAEs and background asthma therapy tolerability
- Measure vital signs (blood pressure, heart rate, respiration rate, body temperature, weight for all patients and height for adolescents only)
- Administer ACQ-7
- Perform spirometry
  - Spirometry will be performed at approximately the same time of last visit after a wash out period of bronchodilators according to their action duration, for example, withholding the last dose of salbutamol/albuterol or levosalbutamol/levalbuterol for at least 6 hours and withholding the last dose of LABA for at least 12 hours (ultra-long acting LABA like vilanterol should be withheld for at least 24 hours) and withholding the last dose of LAMA for at least 24 hours and prior to administration of investigational product. This will be verified before performing the measurements.

- Post-bronchodilator FEV1 should be determined
- Administer health care resource utilization questionnaire
- Perform urine dipstick pregnancy test (for women of childbearing potential)
- Perform blood sampling (fasting if morning visit, prior to administration of IMP) for the following tests:
  - Clinical laboratories and systemic drug concentration
  - Blood sample for pre-vaccine IgG for patients who have signed a specific informed consent for vaccine assessment and who plan to receive a vaccine in the coming 6 weeks (refer to Section 9.3.4)
  - Blood sample for post-vaccine IgG for patients who have signed a specific informed consent for vaccine assessment and who have received a vaccine in the past 3 to 4 weeks (preferred but up to 6 weeks allowed) (refer to Section 9.3.4)
- Download electronic diary/PEF meter and remind patient to bring the device to the next visit
- Call IVRS/IWRS to register visit and obtain treatment kit number
- Dispense and administer IMP
  - Patients will be monitored at the study site for a minimum of 30 minutes after the injection.
  - For those patients willing and trained to perform self-injection: The patient (or caregiver) will perform the injection of IMP under the supervision of the Investigator or delegate.
- Remind patients to use salbutamol/albuterol or levosalbutamol/levalbuterol as reliever medication throughout the study. Instruct patient to record usage in the electronic diary.

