2.4.7 Analyses of vaccine response

For patients who receive vaccination, vaccine IgG in serum prior and after vaccination will be summarized by treatment groups with descriptive statistics.

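### The Visit 6 (Week 8) post-vaccine IgG draw cannot have a permitted pre-vaccine partner, and SAP 2.4.7 names no within-patient measure and no rule for unpaired samples

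*Protocol*

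**What the plan says.** Protocol 9.3.4 describes an optional substudy with two blood samples per vaccination.

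- First sample: "the first should be drawn within 6 weeks prior to vaccination", subject to a lower limit on timing: "Pre-vaccine blood sample collection will not take place until patient is on treatment of IMP for at least 6 weeks". Footnote z of the flow chart in Protocol 1.2 repeats that limit.
- Second sample: "the second should be drawn 3 to 4 weeks after vaccination (up to 6 weeks afterward allowed". Vaccination after 12 weeks of treatment is preferred but not required.

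The visit instructions start with Visit 5 (Protocol 10.1.5, Week 6), which lists a pre-vaccine sample only: "Blood sample for pre-vaccine IgG for patients who have signed a specific informed consent for vaccine assessment and who plan to receive a vaccine" within the next 6 weeks. Visit 6 (Protocol 10.1.6, Week 8) lists a pre-vaccine sample and also a post-vaccine sample for consenting patients "who have received a vaccine in the past 3 to 4 weeks (preferred but up to 6 weeks allowed". Footnote c of the flow chart states: "Visit windows for subsequent visits are +/- 3 days". After permanent treatment discontinuation the window is 5 days either side (Protocol 1.3).

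On analysis, Protocol 11.4.3.2 promises descriptive statistics for vaccine response parameters, which it does not define. SAP 2.4.7 says that "vaccine IgG in serum prior and after vaccination will be summarized by treatment groups with descriptive statistics". SAP 2.1.8 restates the two sampling windows without the 6-week limit.

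**The concern.** There are two gaps, and each would exist without the other.

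The first is a conflict within the protocol. A site following the Visit 6 instruction literally would bleed a patient for a post-vaccine level when Section 9.3.4 barred the matching pre-vaccine sample. The consent is for a pair of samples per vaccine, and one half of that pair could not have been taken as permitted.

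The second is in the SAP. The exploratory objective is the association of vaccine response with treatment, and two samples per vaccination are collected for it. SAP 2.4.7 names the two levels but no quantity that links them within a patient, such as a change or a ratio. It does not mention a breakdown by vaccine, and it does not say what happens to a sample without a partner. The section just before it, SAP 2.4.6.2, does name absolute and percent change from baseline for the biomarkers. At stake is whether the vaccine tables can be read as a response at all, and whether stray post-vaccine values shift them.

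**Working it through.** The documents give no sample size, power or numerical target for vaccine response, so there is no figure to reproduce. The check is a count of days, with the first dose on Day 1.

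**Inputs**
- Earliest pre-vaccine sample: 6 weeks on IMP, so 1 + 42 = Day 43 (Protocol 9.3.4).
- Vaccination: on the day of the pre-vaccine sample or up to 42 days later (Protocol 9.3.4).
- Post-vaccine sample: 21 to 42 days after vaccination (Protocol 9.3.4).
- Visit targets: Visit 5 on Day 43, Visit 6 on Day 57, Visit 7 on Day 71 (SAP Table 9).
- Windows: 3 days on treatment, 5 days after discontinuation.

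**Earliest sample that can be paired.** Vaccination on the day of the earliest pre-vaccine sample gives 43 + 21 = Day 64.

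**Longest gap from Day 43 to each visit**
- Visit 6, nominal: 57 − 43 = 14 days.
- Visit 6, 3-day window: 60 − 43 = 17 days.
- Visit 6, 5-day window: 62 − 43 = 19 days.
- Visit 7, nominal: 71 − 43 = 28 days.

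Every Visit 6 gap is below the 21 days required. Visit 7 (Week 10) is the first scheduled visit that can hold a permitted pair.

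**Which vaccinations the Visit 6 draw serves**
- Nominal date: 57 − 42 = Day 15 to 57 − 21 = Day 36.
- 3-day window: 54 − 42 = Day 12 to 60 − 21 = Day 39.
- 5-day window: no later than 62 − 21 = Day 41.

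All of these precede Day 43, the first day on which a pre-vaccine sample is allowed. Counting every combination of pre-sample day, vaccination day and post-sample day under these rules gives no feasible pair at Visit 6 with any of the three windows.

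**Robustness.** Suppose Visit 5 takes place 3 days early and the sample is drawn on Day 40, which already breaks the 6-week limit. The gap to Day 60 is 20 days, still too short. Only that premature sample combined with a Visit 6 on Day 62 after discontinuation reaches the minimum (62 − 40 = 22 days).

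**Effect on the SAP summary.** Let *n* patients have both samples, with mean levels X before and Y after. Let *m* further patients have only a post-vaccine sample, with mean U. If *m* = 0, mean after minus mean before is Y − X, the mean rise. If *m* > 0, the after mean is (nY + mU)/(n + m), and

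mean after − mean before = (Y − X) + [m/(n + m)] × (U − Y).

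The extra term is the unpaired share times the difference in post-vaccine level. The documents give neither *m* nor U, so its size is unknown. Even with *m* = 0, the two sets of levels recover the mean rise but not its spread or the share of patients who responded.

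**The case against.** The strongest reply is that little follows in practice. The Visit 6 bullet looks like template text, since the same line recurs at later visits where it is sound. The flow chart marks Visit 6 only with footnote z, which carries the 6-week limit, so the chart does not contradict 9.3.4. The consent wording treats the two samples as a pair, vaccination is preferred after Week 12, and sites sample under the protocol, so the SAP's silence on the 6-week limit changes nothing at the site. All of this stands and keeps the point small. It does not remove the conflict, because 10.1.6 read literally still asks for the draw. Unscheduled visits do not help either, since the 6-week limit applies to them too. The 3-week minimum is worded as a recommendation, but the only relaxation offered is upward, to 6 weeks.

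On the SAP, a reader might infer that the plan analyses the two levels separately and rules out the rise. The documents do not support that. SAP 2.4.7 does not say so, and the undefined parameters in Protocol 11.4.3.2 leave room for a change or a ratio. What stands is narrower: no within-patient measure is named, although the biomarker section names one.

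**Conclusion.** The schedule conflict is established: under the 6-week limit, the 3-week minimum and either visit window, a Visit 6 post-vaccine sample cannot be paired. The SAP gap is established in its narrow form: only levels are named, and nothing keeps unpaired values out of the post-vaccination summary.

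Three stronger readings should be resisted.

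- The Visit 6 entry does not cause the SAP gap; they are separate.
- It cannot be said that the before and after summaries will describe different patients. That depends on how many Visit 6 draws are made, which the documents do not show.
- No gain in precision is claimed. It would depend on a correlation between the two samples that the documents do not give, and no standard error or interval is planned for this analysis.

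The impact is minor. One visit is affected, participation is optional, the objective is exploratory, and vaccine response is not in the SAP testing hierarchy (Table 6).

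**What to change.** 1. Reconcile Protocol 10.1.6 with Section 9.3.4. With the 6-week limit kept, this means removing the post-vaccine draw from Visit 6, so that Visit 7 (Week 10) is the first scheduled visit to list it.
2. In SAP 2.4.7, add a descriptive summary of the paired post/pre ratio for each vaccine antigen and treatment group, for example the geometric mean fold rise with a 95% confidence interval. Restrict it to patients with both samples inside the 9.3.4 windows.
3. State in the same section that unpaired values are listed and not summarised.

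The cost is one bullet in the protocol and a few lines in the SAP. No additional samples are needed. The downside is that a few unpaired values leave the summary.

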#### **9.4 FUTURE USE OF SAMPLES**

Not all of the samples collected during this study may be required for the tests planned in this clinical trial. For subjects who have consented to it, the samples that are archived, unused or left

over after planned testing may be used for additional research purposes (any genetic analysis subject to additional consent per Section 9.3.3). For subjects who have consented to it, archival blood samples will be collected at the visit specified in the study flow chart, 15 mL each, will be collected into a dry, red topped tube (or into smaller tubes of equivalent total volume) kept at room temperature for 30 minutes and then centrifuged at approximately 1500 g for 10 minutes at room temperature. The serum will then be transferred, in equal portions, into 3 storage tubes, which will be immediately capped and frozen in an upright position at -20°C or colder.

These archived serum samples, and any residual or leftover serum, plasma or blood remaining from planned laboratory work, may be used for research purposes related to asthma (eg, exploratory biomarkers of disease or drug effect), additional drug safety assessments or development and validation of bioassay methods beyond those defined in the present protocol. These samples will remain labelled with the same identifiers as the ones used during the study (ie, subject ID, sample ID). They will be transferred to a Sanofi site (or a subcontractor site) which can be located outside of the country where the study is conducted. The Sponsor has included safeguards for protecting subject confidentiality and personal data (see Section 14.3 and Section 14.5).

## **9.5 APPROPRIATENESS OF MEASUREMENTS**

The efficacy and safety assessments used in this study are standard for the evaluation of therapy in patients with asthma.

## 10 STUDY PROCEDURES

### 10.1 VISIT SCHEDULE

The clinical trial consists of three periods, using an add-on therapy approach to inhaled corticosteroid in combination with one or two other controller medications:

- Screening Period (4±1 weeks; Visit 1)
- Randomized Treatment Period ( 52 weeks; Visits 2-18)
- Post-treatment Period (12 weeks; Visits 19-21)

The study visits occur on the planned dates (relative to the first injection), as scheduled. The visit schedule should be adhered to within the ± 3 day visit window.

All the study visits should be scheduled in the morning, to have the spirometry performed and the patient should be fasting for serum chemistry tests. However, if the visit can only be done at a different time of the day and the patient is not fasting, then he/she should be advised to have a light meal and the site should document that serum chemistry was not obtained under fasting conditions. For spirometry, it should be performed at approximately the same time of the day at each visit throughout the study.

Patients who permanently discontinue the study medication will be asked and encouraged to return to the clinic for study visits and participate in assessments according to the visit schedule until the end of the study with a +/-5 day window (See Section 1.3). Under exceptional circumstances when a patient cannot come to the site for the scheduled visit, a phone contact can be made after sponsor approval is given. During the phone contact, at least information about AEs, concomitant medication and asthma exacerbation events should be collected.

Patients who discontinue early from treatment or patients who choose not to participate in the OLE study may be asked to return to the clinic to have additional ADA samples collected for analysis based on the overall assessment of antibody titers and/or clinical presentation at the time of discontinuation or at the time of last study visit.

Reminder: sexually active female patients of reproductive potential are required to practice an effective contraception throughout the participation in the study including a 12-week period after last IMP dose. Sites should counsel these patients, with special attention towards adolescent patients regarding the importance of practicing responsible and effective contraception throughout the participation in the study including a 12-week period after last IMP dose.

Prior to all screening assessments, after discussion of participation in the study, the written consent form (including voluntary participation in pharmacogenetic testing/future use of blood samples/vaccination testing) must be signed and dated.

Although the screening assessments for this study are grouped under the heading of a single visit in this protocol, it is possible for them to be performed over more than 1 site visit if necessary, as

long as the screening visit window prior to randomization (Day 1) is respected. If certain dynamic laboratory tests do not meet the eligibility criteria, these laboratory assessments may be repeated, at the discretion of the investigator, if it is judged to be likely to return to acceptable range for study inclusion within the screening visit window (35 days) prior to Day1. These patients do not need to sign a new ICF and be allocated a new patient number within this same screening window.

Patients that fail the initial screening for exclusion criteria, eg, concomitant medications, may be rescreened for study eligibility 1 additional time. Patients that are re-screened must sign a new consent form and will be allocated a new patient number; all of the Visit 1 procedures must be repeated (refer to Section 8.4 for further instructions related to rescreening) unless a prior assessment is performed within the time frame permitted prior to study entry.

Patients that fail the Screening Visit (Visit 1) or Randomization Visit (Visit 2) because of eDiary /spirometry equipment malfunction, or patient-related / site personnel-related unintentional errors may be rescreened one time after approval is granted by the Sponsor's clinical study director. In every case of rescreen allowance due to technical equipment malfunction and/or unintentional human error(s), the Study Investigator must document receipt of Sponsor approval and when applicable, document the site's corrective action plan to prevent future occurrences.

When approaching the season appropriate for influenza vaccination, patients will be reminded to inform the clinic staff about vaccination plans. Similarly, when approaching the planned date of tetanus (alone or combined), any pneumococcal and any meningococcal vaccination, patients will be reminded about the related pre- and post-vaccination blood sampling for vaccine IgG testing. Those who have not yet signed the separate consent for collection of blood pre-vaccination (eg, those who make mid-study decisions about vaccinations) may do so just prior to blood collection.

It is recommended that assessments/procedures at a site visit are performed in the following order if applicable, and these assessments/procedures should be done prior to IMP administration:

1. Patient-reported outcomes and other questionnaires
2. Procedures:
  - a) ECG
  - b) FENO
  - c) Spirometry
  - d) Reversibility/Post-bronchodilator FEV1
  - e) eDiary download
3. Safety and laboratory assessments
4. IMP administration

